Appendix 1: Cohort 1 Schedule of Activities

Assessment	SRN Days -56 to -1	Double-Blind Treatment Period													Move to OLE ^g if applicable	Safety Follow-Up ^a	Unplanned Visit ^b	Tx DC ^a	
		1	2	3	4	5	6	7	8	9	10	11	12	13					
Infusion/Dose Number		1	3 ^d	5	9	13	17	21	25	29	33	37	41	45	49 ^e		-	-	-
Week			(±3)	(±5)	(±5)	(±5)	(±5)	(±5)	(±5)	(±5)	(±5)	(±5)	(±5)	(±5)	(±5)	57	-	-	-
(Visit window in days)																(±7)	-	(±7)	
[¹⁸ F]GTP1 PET ^m		x													x		x ⁱ		
ECG ^o	x ^p		x		x										x		x ⁱ		
Hematology ^q	x ^p		x		x		x		x		x		x		x	x	x	x	
Chemistry, lipids, coagulation ^r	x ^p		x		x		x		x		x		x		x	x	x	x	
HbA _{1c} , B12, folic acid, TSH, T4	x ^p																		
Viral serology ^s	x ^p																		
Pregnancy test ^t	x	x	x	x	x	x	x	x	x	x	x	x	x	x	x	x	x	x	
Urinalysis ^u	x ^p		x			x			x		x		x		x		x	x	
Study drug administration			x	x	x	x	x	x	x	x	x	x	x	x	x	x	x	x	
Serum PK sample ^v			x	x	x	x	x			x			x		x		x ⁱ		
Serum ADA sample ^{v, w}		x				x			x			x		x		x	x ⁱ		
Blood sample for APOE	x																		
Blood sample for WGS/SNP ^x		x																	
Blood sample for biomarkers ^v		x	x	x	x	x	x		x			x		x		x	x ⁱ		
CSF sample for PK and biomarkers (if applicable) ⁿ	x	x ^y														x	x ⁱ	x ⁱ	
Concomitant medications ^z	x	x	x	x	x	x	x	x	x	x	x	x	x	x	x	x	x	x	
Adverse events ^{aa}	x ^{aa}	x	x	x	x	x	x	x	x	x	x	x	x	x	x	x	x ^{aa}	x	

See [Appendix 2](#) for OLE, if patient continues

Appendix 1: Cohort 1 Schedule of Activities

[¹⁸F]GTP1=fluorine-18 Genentech tau probe 1; A_β=β-amyloid; AD=Alzheimer's disease; ADA=anti-drug antibody; ADAS-Cog11=Alzheimer's Disease Assessment Scale—Cognitive Subscale, 11-item version; ADCS-ADL=Alzheimer's Disease Cooperative Study—Activities of Daily Living Inventory; C-SSRS=Columbia-Suicide Severity Rating Scale; CaGI-Alz=Caregiver Global Impression Scales for Alzheimer's disease; CDR=Clinical Dementia Rating; COA=clinical outcome assessment; CSF=cerebrospinal fluid; DC=discontinuation; DVF=Diagnostic Verification Form; eCRF=electronic Case Report Form; HbA_{1c}=hemoglobin A_{1c}; HBsAg=hepatitis B surface antigen; HCV=hepatitis C virus; LP=lumbar puncture; MMSE=Mini-Mental State Examination; MRI=magnetic resonance imaging; NPI=Neuropsychiatric Inventory; OLE=open-label extension; PET=positron emission tomography; PK=pharmacokinetic; SNP=single nucleotide polymorphism; SRN=screening; T4=thyroxine; TSH=thyroid-stimulating hormone; Tx=treatment; WGS=whole genome sequencing.

Notes: All postbaseline study visits must be scheduled in reference to the first dosing day (Week 1 visit). All activities/assessments in a given study visit must be performed within ±5 days of the scheduled visit, unless otherwise specified (e.g., [¹⁸F]GTP1 PET scans). On study drug administration visits that span multiple days, study drug administration must occur on the last day.

On study drug administration days:

- All assessments must be performed prior to dosing, unless otherwise specified
- Pre-infusion laboratory samples should be drawn 0–4 hours before the start of infusion, unless otherwise specified
- Post-infusion laboratory samples should be drawn 0–30 minutes after the end of infusion, unless otherwise specified

During the COVID-19 pandemic, study visit activities, excluding imaging assessments, can be performed in the patient's home or in an approved alternate location. Selected COAs can be administered remotely (by telephone or video call), as outlined in the Study GN40040 remote COA administration guidance. Deviations from the schedule of activities will be documented as COVID-19-related protocol deviations.

^a Patients who complete the double-blind treatment period and who do not enroll into the OLE treatment period will return to the clinic for a treatment completion visit (safety follow-up) at Week 57 (±7 days). Patients who discontinue study drug (MTAU9937A or placebo) prematurely in the double-blind treatment period will return to the clinic for a treatment discontinuation visit 12 weeks (±7 days) after the final dose of study drug.

^b Visit not specified by the protocol. Additional assessments (possibly including PK sample collection) should be performed as clinically indicated. Patients who miss study drug infusions during the double-blind treatment period for reasons related to the COVID-19 pandemic may have additional COAs administered remotely (by telephone or video call) at the time of the first missed infusion and at the time when in-clinic study drug infusions resume. Refer to the Study GN40040 COA Manual and remote COA administration guidance for specific COA assessments to be administered and order of administration.

Appendix 1: Cohort 1 Schedule of Activities

- c The baseline visit period must begin after enrollment (randomization) and may be split over multiple visit days; the first and last visit days of the baseline period must be separated by no more than 14 days from each other (e.g., the baseline visit period may start on a Monday and end on the Monday 2 weeks later). All COA assessments during the baseline visit period should be performed as close to the last visit day of the baseline period as possible. COA assessments, [¹⁸F]GTP1 PET scan, and LP from the baseline visit period may be performed on the same day that study drug is first administered (on the Week 1 visit), but they must be performed prior to dosing. All activities specified for the Week 1 visit (the first dosing visit) must be performed on the same day and must occur no later than 15 days after the baseline visit period begins (e.g., if the first baseline visit period day is a Monday, then the first dosing of study drug must occur no later than the Tuesday 2 weeks later). Extensions to the 15-day baseline visit period (e.g., to complete [¹⁸F]GTP1 PET imaging) may be granted on a case-by-case basis by the Medical Monitor.
- d At this visit, all activities/assessments must be performed within ± 3 days of the scheduled visit.
- e At Week 49, patients will move to OLE or will be scheduled for a treatment completion visit (safety follow-up).
- f Informed consent must be documented before any study-specific screening procedure is performed. Informed consent with the Early Screening Informed Consent Form permits MMSE, medical history, AD history, personal status, and demographics. Informed consent with the main Informed Consent Form is required for all other study-specific screening procedures.
- g Medical history includes clinically significant diseases, surgeries, cancer history (including prior cancer therapies and procedures); reproductive status; smoking history; use of alcohol and drugs of abuse; recent history (5 years) of non-elective hospitalizations, pneumonia or cardiovascular events; lifetime use of any A β -targeting therapies; and all medications (e.g., prescription drugs, over-the-counter drugs, vaccines, herbal/homeopathic remedies, nutritional supplements) used by the patient within 3 months prior to the initiation of screening. Demographics include age, sex, self-reported race/ethnicity (as permitted by local regulations), handedness, and years of education. Demographics of caregiver will also be collected with exception of handedness.
- h Refer to the Study GN40040 COA Manual for instructions on COA administration order, specification of list versions to use at each visit, rater roles, restrictions on raters, and additional details on COA administration and the endpoint reliability program. At all visits, all COA questionnaires/scales (excluding the DVF) will be rater administered before the patient, rater, or caregiver receives any information on disease status, prior to LPs scheduled in the visit, and prior to the administration of study drug. In addition, on any given day when COAs are performed, all COAs (with the exception of the DVF and the C-SSRS) must be performed prior to non-COA assessments, study drug, and [¹⁸F]GTP1 radioligand or amyloid radioligand unless otherwise specified. For details on permitted concomitant medication use prior to COA assessments, see Section 4.1.2.
- i Only perform assessment if discontinuation visit is ≥ 16 weeks after last assessment for this instrument or procedure. However, if the patient discontinues study drug because of an infusion-related reaction, concurrent ADA and PK samples will also be collected at 12 weeks after the final administration of the study drug. An [¹⁸F]GTP1 scan should only be performed if at least 24 weeks has elapsed since any previous [¹⁸F]GTP1 scan and local annual radiation limits have not been exceeded.

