2.2 SAFETY OBJECTIVES

The safety objectives for this study are to evaluate the safety and tolerability of MTAU9937A compared with placebo on the basis of the following endpoints:

- Nature, frequency, severity, and timing of adverse events and serious adverse events, with severity determined according to WHO toxicity grading scale
- Changes from baseline in vital signs, physical findings, neurologic findings, ECG, and clinical laboratory results during and following MTAU9937A administration
- Changes from baseline in suicidal ideation and behavior during and following MTAU9937A administration as assessed by the Columbia-Suicide Severity Rating Scale (C-SSRS)
- Nature, frequency, severity, and timing of neuroimaging abnormalities that could represent cerebral vasogenic edema and/or microhemorrhage, during MTAU9937A administration

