4.6 TREATMENT, PATIENT, STUDY, AND SITE DISCONTINUATION

4.6.1 Study Treatment Discontinuation

Patients must permanently discontinue study treatment if they experience any of the following:

- Any medical condition that the investigator or Sponsor determines may jeopardize the patient's safety if he or she continues to receive study treatment
- Investigator or Sponsor determination that treatment discontinuation is in the best interest of the patient
- Pregnancy

The primary reason for study treatment discontinuation should be documented on the appropriate eCRF. Patients who discontinue study treatment prematurely will not be replaced.

Patients will return to the clinic for a treatment discontinuation visit 12 weeks (± 7 days) after the final dose of study drug (see [Appendix 1–Appendix 4](#) for additional details).

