Appendix 1: Cohort 1 Schedule of Activities

- j Includes respiratory rate, pulse rate, and systolic and diastolic blood pressure while the patient is in a seated position, and temperature. Vital sign assessments should be performed just prior to study drug administration. On study drug treatment visits, vital signs should be collected 0–4 hours prior to infusion and 60–90 minutes after completion of infusion. Vital signs should also be assessed within 1 hour prior to injection of [¹⁸F]GTP1 or initiation of the LP procedure and within 1 hour after injection of [¹⁸F]GTP1 or the completion of the LP procedure. Record abnormalities observed at baseline on the General Medical History and Baseline Conditions eCRF. At subsequent visits, record new or worsened clinically significant abnormalities on the Adverse Event eCRF.
- k Includes evaluation of the head, eyes, ears, nose, and throat, and the cardiovascular, dermatologic, respiratory, and gastrointestinal systems. In addition, the musculoskeletal and genitourinary systems should be examined as clinically indicated. Record abnormalities observed at baseline on the General Medical History and Baseline Conditions eCRF. At subsequent visits, record new or worsened clinically significant abnormalities on the Adverse Event eCRF.
- l Perform a limited, symptom-directed examination at specified timepoints or as clinically indicated. Record new or worsened clinically significant abnormalities on the Adverse Event eCRF.

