Appendix 3: Cohort 2 Schedule of Activities

- i Refer to the Study GN40040 COA Manual for instructions on COA administration order, specification of list versions to use at each visit, rater roles, restrictions on raters, and additional details on COA administration and the endpoint reliability program. At all visits, all COA questionnaires/scales (excluding the DVF) will be rater administered before the patient, rater, or caregiver receives any information on disease status, prior to LPs scheduled in the visit, and prior to the administration of study drug. In addition, on any given day when COAs are performed, all COAs (with the exception of the DVF and the C-SSRS) must be performed prior to non-COA assessments, study drug, and [¹⁸F]GTP1 radioligand or amyloid radioligand unless otherwise specified. For details on permitted concomitant medication use prior to COA assessments, see Section 4.1.2.
- j Only perform assessment if discontinuation visit is \geq 16 weeks after last assessment for this instrument or procedure. However, if the patient discontinues study drug because of an infusion-related reaction, concurrent ADA and PK samples will also be collected at 12 weeks after the final administration of the study drug. An [¹⁸F]GTP1 scan should only be performed if at least 24 weeks has elapsed since any previous [¹⁸F]GTP1 scan and local annual radiation limits have not been exceeded.
- k Includes respiratory rate, pulse rate, and systolic and diastolic blood pressure while the patient is in a seated position, and temperature. Vital sign assessments should be performed just prior to study drug administration. On study drug treatment visits, vital signs should be collected 0–4 hours prior to infusion and 60–90 minutes after completion of infusion. Vital signs should also be assessed within 1 hour prior to injection of [¹⁸F]GTP1 or initiation of the LP procedure and within 1 hour after injection of [¹⁸F]GTP1 or the completion of the LP procedure. Record abnormalities observed at baseline on the General Medical History and Baseline Conditions eCRF. At subsequent visits, record new or worsened clinically significant abnormalities on the Adverse Event eCRF.

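### Vital signs at the double-blind discontinuation visit depend on a 16-week gap that an on-schedule visit, 11 to 13 weeks after the last infusion, cannot reach

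*Combined protocol and SAP*

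**What the plan says.** Footnote i of Appendix 1 governs marked cells at the discontinuation visit: "Only perform assessment if discontinuation visit is ≥ 16 weeks after last assessment for this instrument or procedure". Footnote j of Appendix 3 sets the same threshold for Cohort 2: "16 weeks after last assessment for this instrument or procedure". In each appendix the last mark in the vital-signs row carries that letter.

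Appendix 1 footnote a fixes the timing as a "treatment discontinuation visit 12 weeks (±7 days) after the final dose of study drug", and Section 4.6.1 agrees: "Patients will return to the clinic for a treatment discontinuation visit 12 weeks".

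At dosing visits, "vital signs should be collected 0–4 hours prior to infusion and 60–90 minutes after completion of infusion" (Appendix 1 footnote j, repeated as footnote k in Appendix 3). The same footnote adds a separate trigger: "Vital signs should also be assessed within 1 hour prior to injection of [¹⁸F]GTP1 or initiation of the LP procedure", with a matching measurement afterwards. The 16-week footnote also sets its own interval for tau PET: "An [¹⁸F]GTP1 scan should only be performed if at least 24 weeks has elapsed since any previous [¹⁸F]GTP1 scan".

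Section 2.2 lists as a safety endpoint: "Changes from baseline in vital signs, physical findings, neurologic findings, ECG, and clinical laboratory results during and following MTAU9937A administration". Section 6.5 commits to summarizing vital-sign changes from baseline by treatment group.

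**The concern.** A recency condition makes sense for assessments done a few times a year, because it avoids repeating a recent test. Vital signs are measured at every infusion, so the last set is always recent when the patient returns 12 weeks later. Applied to them, the condition switches off the cell that it qualifies.

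The endpoint in Section 2.2 covers the time after treatment as well as during it. Section 1.2.2 gives a plasma half-life of 22.8 to 45.7 days, so 84 days is 84/45.7 = 1.8 to 84/22.8 = 3.7 half-lives, and drug may still be present at the visit. Post-treatment vital signs for early stoppers would be collected only when another procedure or event prompts them. The patients with no such scheduled prompt are those who stopped earliest, a group that would include anyone stopping because of an early reaction.

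**Working it through.** The plan states no figure to reproduce here. The check is interval arithmetic on the schedules.

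**Inputs**
- Threshold: 16 weeks (Appendix 1 footnote i; Appendix 3 footnote j).
- Discontinuation visit: final dose + 12 weeks, ±1 week (Appendix 1 footnote a; Appendix 3 footnote a; Section 4.6.1).
- Last scheduled vital signs: the day of the final dose (Appendix 1 footnote j; Appendix 3 footnote k).
- Infusion weeks: 1, 3, 5, 9, then every 4 weeks to 45 (Cohort 1) or 57 (Cohort 2).
- GTP1 scan interval: 24 weeks, with the previous scan at baseline, on or before Week 1.

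**Check of the 12-week rule.** 45 + 12 = 57 and 57 + 12 = 69. These match the stated safety follow-up weeks for the two cohorts.

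**Vital-signs gap.** Gap = (final dose + 12 ± 1) − final dose = 11 to 13 weeks. The final-dose week cancels, so the result is the same for every dose in both cohorts. The shortfall is 16 − 13 = 3 weeks at best.

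**When a scan would bring vital signs with it.** Weeks since Week 1 at the nominal visit = final dose + 12 − 1.

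| Final dose (week) | Nominal visit (week) | Vital-signs gap (weeks) | 16 reached? | Weeks since Week 1 | Scan interval of 24 reached? |
|---|---|---|---|---|---|
| 1 | 13 | 11–13 | no | 12 | no |
| 3 | 15 | 11–13 | no | 14 | no |
| 5 | 17 | 11–13 | no | 16 | no |
| 9 | 21 | 11–13 | no | 20 | no |
| 13 | 25 | 11–13 | no | 24 | yes |
| 17 | 29 | 11–13 | no | 28 | yes |
| 45 | 57 | 11–13 | no | 56 | yes |
| 57 | 69 | 11–13 | no | 68 | yes |

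The scan column uses nominal timing. For a final dose at Week 9, a baseline scan about 2 weeks before Week 1 and a closing scan at the end of its ±14-day window would give 20 + 2 + 2 = 24 weeks, which just reaches the interval.

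**Other ways to meet 16 weeks.** The visit would have to be at least 3 weeks past its window (13 + 3 = 16). Alternatively, vital signs were missed at the final infusion of a 4-weekly interval, so the gap runs from the infusion before: 4 + 11 to 4 + 13 = 15 to 17 weeks. Both are deviations.

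**The footnote works elsewhere.** The MMSE is done at baseline and then Week 25. With a final dose at Week 17 the visit is at Week 29, and the gap from Week 1 is 28 weeks, so the condition is met.

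**Comparison within the documents.** The closing marks for weight, examinations and routine blood tests in Appendix 1 carry no such condition. Nor do the vital-signs rows of the open-label schedules (Appendices 2 and 4).

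**The case against.** The strongest objection concerns where the mark sits. Column alignment is lost in the text available. In Appendix 1 the marked vital-signs cell, counted literally, could fall under Week 57 rather than the discontinuation visit. This caveat stands, and the original table should be checked. Two things support the reading used here. The footnote's own words confine it to the discontinuation visit. The letter on the mark also changes from i to j between the appendices exactly as the 16-week footnote does, while the general vital-signs footnote moves separately from j to k. A misread superscript would be unlikely to follow that relettering.

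Second, a reader might infer that vital signs are never taken at this visit, or that every double-blind discontinuer lacks them. The documents do not support that. Vital signs are required around a GTP1 injection or lumbar puncture without any 16-week condition, and a scan is generally due from a final dose at Week 13 on. It remains subject to radiation limits and may fall on another day. The lumbar puncture is optional.

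Third, acute harm is covered elsewhere: vital signs 60 to 90 minutes after each infusion, monitoring of infusion reactions until Grade 1 or resolved (Section 5.1.3.2), assessments when clinically indicated, and adverse event follow-up until resolved or stable (Section 5.5.1). This also stands. The gap is in routine post-treatment data, not in the management of reactions.

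**Conclusion.** As written, the scheduled vital signs at the double-blind discontinuation visit cannot fall due within the visit window in either cohort: the gap is 11 to 13 weeks against a required 16. This assumes that the mark belongs to the discontinuation column and that vital signs were taken at the final infusion as scheduled. In practice the gap concerns patients with a final dose at Weeks 1 to 9 and no lumbar puncture, for whom no routine vital signs are called for at that visit at nominal timing. For later stoppers the data depend on whether a scan or lumbar puncture is done.

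The number of patients affected cannot be derived from the documents. A reader might multiply 260 by the 10% in Section 6.1, but that is a dropout allowance for sample size. It is not a rate of stopping treatment and then attending a 12-week visit.

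The closing ECG mark carries the same footnote, but there the condition acts as an ordinary recency filter. With ECGs at Weeks 1 and 5, final doses at Weeks 1, 3 and 5 give nominal gaps of 12, 14 and 12 weeks, so those patients have no routine closing ECG. A final dose at Week 9 gives 16 weeks, and later doses give more. Since that rule can be met for most final doses, changing it would be a preference rather than a correction.

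The vital-signs defect is small but real, and it bears on a stated safety endpoint.

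**What to change.** Reconcile the vital-signs discontinuation cell with the 16-week footnote in Appendices 1 and 3. The simplest way is to remove mark i (Appendix 1) and mark j (Appendix 3) from that cell only, and to leave the footnote on the other rows. This would match the open-label vital-signs rows and the unconditional weight, examination and laboratory marks at the same visit.

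The cost is one footnote mark in each of two tables and a few minutes at a visit already taking place. The summary of changes for Version 5 already reports a double-blind tau PET result, so some or all of these visits may be over. In that case the sponsor should count the double-blind discontinuers without vital signs at this visit and report the number with the safety summaries.

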Appendix 1: Cohort 1 Schedule of Activities

- j Includes respiratory rate, pulse rate, and systolic and diastolic blood pressure while the patient is in a seated position, and temperature. Vital sign assessments should be performed just prior to study drug administration. On study drug treatment visits, vital signs should be collected 0–4 hours prior to infusion and 60–90 minutes after completion of infusion. Vital signs should also be assessed within 1 hour prior to injection of [¹⁸F]GTP1 or initiation of the LP procedure and within 1 hour after injection of [¹⁸F]GTP1 or the completion of the LP procedure. Record abnormalities observed at baseline on the General Medical History and Baseline Conditions eCRF. At subsequent visits, record new or worsened clinically significant abnormalities on the Adverse Event eCRF.
- k Includes evaluation of the head, eyes, ears, nose, and throat, and the cardiovascular, dermatologic, respiratory, and gastrointestinal systems. In addition, the musculoskeletal and genitourinary systems should be examined as clinically indicated. Record abnormalities observed at baseline on the General Medical History and Baseline Conditions eCRF. At subsequent visits, record new or worsened clinically significant abnormalities on the Adverse Event eCRF.
- l Perform a limited, symptom-directed examination at specified timepoints or as clinically indicated. Record new or worsened clinically significant abnormalities on the Adverse Event eCRF.
- m If MRI, amyloid PET, or [¹⁸F]GTP1 PET scan occurs at the same visit as COAs, neuroimaging must be performed after administration of COAs (with the exception of the DVF and the C-SSRS). Only one PET scan should be performed on a given day. Postbaseline [¹⁸F]GTP1 PET scans should be performed \pm 14 days of the scheduled visit; however, extensions to [¹⁸F]GTP1 PET scan windows may be granted on a case-by-case basis by the Medical Monitor. Week 49 visit or treatment discontinuation visit [¹⁸F]GTP1 PET scan dates may be coordinated by the [¹⁸F]GTP1 distribution network on the basis of tracer availability and may be scheduled outside the \pm 14-day window around the scheduled visit if appropriate extenuating circumstances arise. If, at any time, local restrictions for radiation exposure disallow performing a [¹⁸F]GTP1 PET scan within this window, the site should contact the Sponsor to discuss alternative timing. The MRI should be performed and assessed locally and in real time prior to any study drug dosing at the corresponding study visit. Study drug should be withheld if there are clinically significant new or clinically significant worsened MRI abnormalities identified in the local MRI interpretation. However, if no such abnormalities are identified, the dose may be given prior to receipt of the central MRI report (see Section 5.1.1.2). During the COVID-19 pandemic, if an MRI cannot be obtained, the patient should be monitored for any signs or symptoms suggestive of new, clinically significant neurologic abnormalities. If no new, clinically significant abnormalities are observed, study drug may be administered without an MRI, but a subsequent unscheduled study-associated MRI should be obtained as local conditions allow. If new, clinically significant neurologic abnormalities are observed, study drug should be withheld and the patient should be referred for appropriate follow-up and medical treatment, including, if appropriate, an MRI.

